#### **7.2.6.5.1 Unexpected fatal or life-threatening suspected adverse reaction reports**

The sponsor must also notify FDA of any unexpected fatal or life-threatening suspected adverse reaction as soon as possible but in no case later than 7 calendar days after the sponsor's initial receipt of the information.

#### **7.2.6.5.2 Reporting format or frequency**

FDA may require a sponsor to submit IND safety reports in a format or at a frequency different than that required under this paragraph. The sponsor may also propose and adopt a different reporting format or frequency if the change is agreed to in advance by the director of the FDA review division that has responsibility for review of the IND.

#### **7.2.6.5.3 Investigations of marketed drugs**

A sponsor of a clinical study of a drug marketed or approved in the United States that is conducted under an IND is required to submit IND safety reports for suspected adverse reactions that are observed in the clinical study, at domestic or foreign study sites. The sponsor must also submit safety information from the clinical study as prescribed by the post marketing safety reporting requirements.

#### **7.2.6.5.4 Reporting study endpoints**

Study endpoints (e.g., mortality or major morbidity) must be reported to FDA by the sponsor as described in the protocol and ordinarily would not be reported under **Section 7.4.6**. However, if a serious and unexpected adverse event occurs for which there is evidence suggesting a causal relationship between the drug and the event (e.g., death from anaphylaxis), the event must be reported under Serious and unexpected suspected adverse reaction as a serious and unexpected suspected adverse reaction even if it is a component of the study endpoint (e.g., all-cause mortality).

### **7.2.7. Follow-up of Adverse Events/Serious Adverse Events**

All AEs and SAEs documented at a previous visit that are designated as either recovering/resolving or not recovered/resolved, will be reviewed by the Investigator at subsequent visits.

All AEs will be followed until resolution of AE, completion of the subject's participation, or study termination, whichever occurs first.

Serious AEs and AEs resulting in discontinuation will be followed until one of the following occurs:

- The event resolves.
- The event stabilizes.
- The event returns to a baseline value, if a baseline value is available.
- The event can be attributed to agents other than the study drug or to factors unrelated to study conduct.
- The Investigator agrees that follow-up is no longer necessary.

Follow-up reports from the Investigator must be provided as indicated using the SAE report form within **24 hours** of the Investigator's first knowledge of the new information. Additional information (i.e., hospital records, laboratory, or other diagnostic test results) should be provided if requested and/or indicated.

Rules for AE/SAE follow up apply to all subjects, including those who withdraw consent prior to study completion (to the extent allowed). The Investigator will ensure that follow up includes further investigations to elucidate the nature and/or causality of the AE/SAE. These investigations must be consistent with appropriate medical management and subject consent.

Investigators are not obligated to actively seek AEs or SAEs in former study subjects that occur pursuant to the follow-up period. However, if the Investigator or designee learns of any AE or SAE at any time after a subject has been discharged from the study and the event is considered as reasonably related to the study drug, the Investigator will notify the Sponsor.

## 8 Statistical Analysis Plan

### 8.1 Study Design

This is a non-randomized phase II single arm Simon's minimax two-stage study of neoadjuvant nivolumab and CMP-001. Nivolumab (I.V.) and CMP-001 (intra-tumorally) will be administered for 7 weeks pre-operatively (weeks 1-7) followed by planned surgical resection at week 8-10. Following recovery from surgery, nivolumab (I.V.) and CMP-001 (S.C. or peri-tumoral resection site) will commence and continue for 48 weeks. Details for the two-stage design are in **Section 8.3**.

### 8.2 Safety Monitoring

The PD-1/CMP-001 combination has been tested in the PD-1 refractory setting in melanoma including in a phase I study that evaluated multiple doses of CMP-001 including 5mg, 7.5mg and 10mg. The safety profile observed thus far suggests that the **risk of additive toxicities are unlikely to be significantly increased** in the neoadjuvant setting. Further, the dose being tested in this study (5mg) is 50% the ceiling dose tested in other CMP-001 studies in combination with PD-1 inhibitors, none of which reported a toxicity rate >33%.

However, in the context of this neoadjuvant trial, we will monitor dose limiting toxicities (DLTs) for 4 weeks for the 1st 3 patients accrued. DLT is defined as any adverse event(s) (AEs) considered possibly, probably, or definitely related to the CMP-001 plus nivolumab regimen, which occur during the first 15 days of therapy (i.e. following 3 doses of CMP-001; W1D1, W2D1, W3D1) IN the Prime phase only. Attribution of AEs specifically to either CMP-001 or nivolumab is challenging, therefore, the relationship to CMP-001 should be based on attribution to the combination of the two drugs. During DLT monitoring period, no further accrual will be permitted. Any patient who has started the studied treatment will be evaluable for safety.

The following AEs will be considered DLTs if deemed related to study therapy:

- Hematologic
  - Grade 4 neutropenia
  - Febrile neutropenia, defined as absolute neutrophil count (ANC)  $\leq 1000/\text{mm}^3$  with a temperature of  $\geq 38.3$  degrees °C
  - Grade  $\geq 3$  neutropenic infection
  - Grade  $\geq 3$  thrombocytopenia with bleeding
  - Grade 4 thrombocytopenia
- Non-hematologic
  - Grade  $\geq 3$  toxicities (non-laboratory)
  - Grade  $\geq 3$  nausea, vomiting or diarrhea despite maximal medical intervention
  - Grade 4 aspartate aminotransferase (AST) and alanine aminotransferase (ALT)

- Other (non AST/ALT) non-hematologic Grade  $\geq 3$  laboratory value if the abnormality leads to overnight hospitalization

IMPORTANT: CMP-001 is designed to specifically bind to Toll like receptor 9 (TLR9) which is expressed in the endosomes of pDCs. Upon activation through TLR9, pDCs will secrete large amounts of type 1 interferons and associated Th1-promoting cytokines. Given this mechanism of action, it is expected that the adverse event profile associated with intratumoral injection of CMP-001 may be similar to that seen after administration of interferons (e.g. flu-like symptoms such as fever, rigors, nausea & vomiting). In addition, given the release of IFN-inducible chemokines and cytokines, symptoms associated with cytokine release, such as chills/rigors, fever, nausea/vomiting and hypotension, may occur within hours of a CMP-001 intratumoral injection. Recommended prophylaxis, outlined above in **Section 5.2.2.1.** may help to minimize the severity of these reactions.

An AE believed to be caused by tumor flare or pseudoprogression does not necessarily need to be considered a DLT. Any such cases that would otherwise meet DLT criteria must be discussed immediately with the Principle Investigator. If the Principle Investigator and Sponsor agree that tumor flare is a likely explanation for the AE, treatment with CMP-001 may continue so long as the subject is closely monitored by the Principle Investigator or study staff while on study.

Subjects who experience a DLT will have CMP-001 and nivolumab dosing withheld until the toxicity has returned to  $\leq$  Grade 1. If the Investigator determines that continued treatment with CMP-001 is in the subject's best interest, treatment may resume at a reduced dose (2.5mg weekly or every 4 weeks; 1 dose level lower) at the same schedule after consultation with the Principle Investigator. If a CMP-001 injection is delayed due to toxicity it should be given as soon as possible once the toxicity has resolved. If a subject experiences DLT on a reduced dose of CMP-001, further accrual will be halted.

Subjects may remain on the same dose of nivolumab. Any dose modification should follow the approved nivolumab label.

The Investigator may escalate the subject back to the original CMP-001 dose level if: 1) the lower dose level was tolerated without any DLTs; 2) Sponsor approval is given.

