##### Preliminary Safety and Efficacy in PD-1 primary Refractory Melanoma

Intratumoral administration of CMP-001 is currently being evaluated in combination with pembrolizumab in subjects with metastatic melanoma resistant to checkpoint inhibitors. In study CMP-001-001, A Multicenter, Open-label Phase 1b clinical Study of CMP-001 in Combination with Pembrolizumab in Subjects with Advanced Melanoma, CMP-001 is being administered intratumorally on a weekly (Schedule A) and Q3W schedule (Schedule B) across a dose range of 1-10 mg. To date, approximately 45 subjects have been treated in the CMP-001-001 study. Preliminary analysis of safety demonstrates an acute toxicity profile that predominantly consists of Grade 1-2 adverse events including mild fever, chills, rigors, nausea, vomiting and occasional hypotension. In some subjects the severity of this adverse event profile is increased. These AEs typically present after the third CMP-001 dose and generally resolve within a few hours with standard supportive care. The mechanism of action associated with the acute toxicity profile appears to resemble symptoms associated with cytokine release. A treatment algorithm has been developed for the management of these reactions and can be found in **Section 5.2.2.7.** CMP-001-001 adverse event summary in Cohort 2 of the Dose Escalation Phase are presented in **Table 4.1.4-1.**

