**Table 4.1.4-1: Related AEs Reported in More than One Subject in CMP-001-001 Study**

CMP001-001 Protocol		
Related AEs Reported in More than One Subject*		
	N (%) of Subjects	
	Schedule A^ (N=28)	Schedule B^^ (n=11)
Anemia	4 (14.3%)	-
Chills	15 (53.6%)	-
Constipation	2 (7.1%)	-
Cough	2 (7.1%)	-
Diarrhea	3 (10.7%)	-

Fatigue	7 (25.0%)	2 (18.2%)
Fever	16 (57.1%)	-
Flushing	2 (7.1%)	-
Headache	6 (21.4%)	2 (18.2%)
Hypertension	2 (7.1%)	-
Hypotension	8 (28.6%)	-
Injection Site Pain	2 (7.1%)	3 (27.3%)
Nausea	8 (28.6%)	-
Pruritus	3 (10.7%)	-
Rigors	6 (21.4%)	-
Tachycardia	2 (7.1%)	-
Vomiting	8 (28.6%)	2 (18.2%)

\*Based on EDC data as of 30 May 2017  
 ^ Schedule A includes Cohort 1 (1 mg, n=3); Cohort 2 (3 mg, n=12); Cohort 4 (5 mg, n=6); Cohort 6 (10 mg, n=3); Cohort 8 (10 mg, n=4)  
 ^^ Schedule B includes Cohort 3 (3 mg, n=4); Cohort 5 (5 mg, n=3); Cohort 7 (10 mg, n=3), Cohort 9 (10 mg, n=1)

Preliminary efficacy data, based upon RECIST investigator reads, from the ITT population across both schedules from the 1, 3 and 5 mg cohorts (N=28) demonstrated on ORR of 21.4% (5 PRs, 1 CR). The ORR in subjects treated on Schedule A (N=21) was 24% (5/21; 95% CI 8.2%-47.2%) and on Schedule B (N=7) was 14.3% (1/7; 95 % CI 0.4-57.9%). All responses seen were evidenced at the subject's first follow up scan (12 weeks). Durability or all responses have been seen beyond 24 weeks with some responses being maintained beyond 1 year.

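### Section 8.2 still describes a 5 mg CMP-001 regimen, so a DLT at the 10 mg intra-tumoral dose has two written restart doses, 7.5 mg and 2.5 mg

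*Combined protocol and SAP*

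**What the plan says.** Section 8.2 (Safety Monitoring) first cites "a phase I study that evaluated multiple doses of CMP-001 including 5mg, 7.5mg and 10mg". It then adds, as a further reason to expect acceptable toxicity, that "the dose being tested in this study (5mg) is 50% the ceiling dose tested in other CMP-001 studies". DLTs are counted in the Prime Phase only, over the first 15 days, "following 3 doses of CMP-001; W1D1, W2D1, W3D1".

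After a DLT, "treatment may resume at a reduced dose (2.5mg weekly or every 4 weeks; 1 dose level lower", following consultation with the Principal Investigator. Two further rules in 8.2 refer to the reduced dose:

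- "If a subject experiences DLT on a reduced dose of CMP-001, further accrual will be halted".
- "The Investigator may escalate the subject back to the original CMP-001 dose level", provided the lower dose was tolerated without a DLT and the Sponsor approves.

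The dosing sections describe a different regimen. Sections 4.2.2, 5.2.2 and 5.3 give 5 mg in week 1 (subcutaneous) and 10 mg intra-tumorally in weeks 2-7. The Boost Phase is 5 mg every 4 weeks, and 5.2.2 calls that dose fixed. Section 5.2.2.4 sends reductions after a CMP-001-related DLT to Table 5.2.2.3-1. Section 5.2.2.7 allows a single reduction and takes a subject off study for a further DLT at Level -1.

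**The concern.** Section 8.2 is where the DLT rules are set out, yet its dose rationale and its restart dose both belong to a regimen in which every CMP-001 dose is 5 mg. Half the ceiling is not a reason to expect low toxicity from intra-tumoral doses given at the ceiling.

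The restart dose has more practical effect. A clinician managing a DLT after a 10 mg injection would find 2.5 mg in 8.2 and 7.5 mg through 5.2.2.4, 5.2.2.7 and the table. Nothing says which section prevails. The off-study rule in 5.2.2.7 names Level -1, so a subject restarted at 2.5 mg under 8.2 is not literally covered by it.

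**Working it through.** **1. The plan's own figure.** The ceiling implied by 8.2 is 5 / 0.50 = 10 mg. This agrees with the 10 mg top dose cited in the same paragraph and with the phase 1b study in 4.1.4, which dosed "across a dose range of 1-10 mg". So 5 / 10 = 50% reproduces, but only for a 5 mg dose.

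**2. The current regimen.** For weeks 2-7 the ratio is 10 / 10 = 100%.

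- Prime Phase: 6 of 7 doses are 10 mg.
- DLT window: W1D1 is 5 mg; W2D1 and W3D1 are 10 mg each. That is 2 of 3 doses, and 20 of 5 + 10 + 10 = 25 mg (80%).

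**3. The restart dose.** Levels from Table 5.2.2.3-1:

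| Level | Dose | Cut from 10 mg |
|---|---|---|
| 1 | 10 mg | 0% |
| -1 | 7.5 mg | 1 - 7.5/10 = 25% |
| -2 | 5 mg | 1 - 5/10 = 50% |
| -3 | 2.5 mg | 1 - 2.5/10 = 75% |

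- DLT on a 10 mg dose: one level down is 7.5 mg. Section 8.2 gives 2.5 mg, three levels down. The two differ by 7.5 / 2.5 = 3 times, or 5 mg per injection.
- DLT on the 5 mg week 1 dose: 2.5 mg is one level down (Level -2 to Level -3), so 8.2 is right for this case. Restarting at 7.5 mg here would be 7.5 / 5 = 1.5 times the dose that caused the DLT.
- Every 4 weeks is the Boost schedule for CMP-001. The 2.5 mg figure in 8.2 is therefore also the only reduced Boost dose written anywhere, and it conflicts with the fixed 5 mg in 5.2.2.

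**4. The rules that follow.** The accrual halt in 8.2 is triggered by a DLT on any reduced dose, so its trigger is the same at 7.5 mg or 2.5 mg. Only the off-study rule in 5.2.2.7 is tied to Level -1.

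**5. Support for 10 mg.** Under Schedule A, Table 4.1.4-1 lists "Cohort 6 (10 mg, n=3); Cohort 8 (10 mg, n=4": 3 + 4 = 7 of 28 subjects (25%). Schedule B has 3 + 1 = 4 of 11 (36%). In all, 11 of 39 subjects (28%) had 10 mg, with pembrolizumab. Section 4.2.2 adds that this study's own run-in saw no rise in adverse events at higher doses.

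**6. Labels in Table 5.2.2.3-1.** Dose over volume is 10/2.0 = 7.5/1.5 = 5/1.0 = 2.5/0.5 = 5.0 mg/mL, which matches the vials in Table 9.1-1. The header says 6 mg/mL. At that strength 2.0 mL would hold 12 mg, above the 10 mg daily limit in 5.2.2.3. The title covers doses 2-6, while 5.2.2 applies the table to weeks 2-7.

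**7. The statistical design.** With p the response probability, the chance of success in the 8.3 design is the sum over x = 5 to 14 of P(Bin(14, p) = x) × P(Bin(16, p) ≥ 13 - x). This gives 0.047 at p = 0.28 and 0.907 at p = 0.55, matching the stated 5% and 0.91. No CMP-001 dose enters the calculation.

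**The case against.** The best defence is that this is leftover wording with little practical effect. The 5 mg sentence is background and directs no dose. Both restart doses are below 10 mg, resuming is optional, and the Principal Investigator must be consulted at a single center. Section 5.2.2.4 points to the table without saying one step, so 2.5 mg is at least a listed level, and following 8.2 gives the lower dose. The formal accrual hold covers only the first 3 patients, and 4.2.2 describes the run-in in the past tense.

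All of this limits the harm. It does not remove the conflict: 8.2 calls 2.5 mg one level lower, which is untrue of 10 mg, and 5.2.2.7 treats Level -1 as the reduced dose. The restart rules apply to any subject with a DLT, not only the first 3, and any consultation would begin from two written doses.

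Three stronger readings are tempting, and the documents do not support them:

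- **That 10 mg lacks safety support.** The same paragraph of 8.2 cites doses up to 10 mg, and step 5 gives two further sources.
- **That the accrual halt is ambiguous.** It applies to a DLT on any reduced dose.
- **That 2.5 mg is simply an error for 7.5 mg.** It is the correct one-level reduction after the week 1 dose, and the only written reduced dose for Boost. Replacing it throughout would let a subject restart above the dose that caused the DLT.

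**Conclusion.** The point holds as an internal contradiction in the current text and should be fixed. Section 8.2 puts the dose at 50% of the ceiling when the intra-tumoral dose is at 100%. It also gives a restart dose after a 10 mg DLT that is a third of the one reached through 5.2.2.4, 5.2.2.7 and the table (2.5 against 7.5 mg). The off-study rule matches only the second of these.

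The conclusion rests on the written text alone, with one reading: that the reduction intended after a DLT is one level, as both 8.2 and 5.2.2.7 indicate. The practical risk is moderate to low because of the required consultation. Sample size, type I error and power do not change.

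**What to change.** In one amendment:

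1. In 8.2, state that the intra-tumoral dose is 10 mg, equal to the ceiling, and that 5 mg applies only to the subcutaneous week 1 and Boost doses. Cite the phase I 10 mg data and the run-in in 4.2.2.
2. In 8.2, set the restart dose by the dose at which the DLT occurred. After a 10 mg intra-tumoral dose, resume at Level -1 (7.5 mg) per Table 5.2.2.3-1. After the 5 mg week 1 dose, keep 2.5 mg, so that no subject restarts above the dose that caused the DLT.
3. Keep 2.5 mg every 4 weeks as the reduced Boost dose, and cross-reference it in 5.2.2, which now calls the Boost dose fixed at 5 mg.
4. In 5.2.2.7, tie the off-study rule to a DLT on the reduced dose, whatever its level.
5. Correct the header of Table 5.2.2.3-1 to 5 mg/mL after a pharmacy check, and its title to doses 2-7.

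The cost is wording in 8.2, 5.2.2 and 5.2.2.7, two table labels and one pharmacy check. It needs no added patients or visits and no change to the two-stage design.

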## **5.2.2 CMP-001 Dose Selection/Modification**

During the Prime Phase, the first dose of CMP-001 (week 1) is fixed at 5mg subcutaneously. Subsequent doses of CMP-001 administered during the Prime Phase (weeks 2-7) will be at 10mg administered intra-tumorally. Should patients develop side effects, intra-tumoral doses during this period of the Prime Phase (weeks 2-7) may be reduced (see **Table 5.2.2.3-1**).

Following resection, during the Boost Phase, the CMP-001 dose is fixed at 5mg injected subcutaneously at the site of the resected tumor.

Rationale for dose selection is provided in **Section 4.2.2 – Rationale for Dose Selection/Regimen/Modification: CMP-001**.

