#### **5.2.2.4    CMP-001 Dose Modification**

CMP-001 will be dose-reduced in patients who develop CMP-001 related DLT and resume study therapy with Nivolumab/CMP-001 combination if Investigator determines that continued treatment with CMP-001 is in the subject's best interest. In this event, CMP-001 will be dose reduced as in **Table 5.2.2.3-1**.

[figure not shown]
CMP-001 will be withheld for CMP-001 related Grade 4 hematologic toxicities, non-hematological toxicity  $\geq$  Grade 3 including laboratory abnormalities, and severe or life-threatening AEs.

If CMP-001 is permanently discontinued for, subjects may continue to receive Nivolumab.

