#### 5.2.2.7 Management of CMP-001 toxicity

##### CMP-001 Associated Adverse Events

If subjects develop inflammation at the injection site this may be managed using cold compresses and/or acetaminophen or non-steroidal anti-inflammatory agents. If flu-like symptoms (i.e., fever, myalgia, and headache) arise, these may be managed using acetaminophen or non-steroidal anti-inflammatory agents.

[figure not shown]
It is expected that symptoms associated with a large release in cytokines at the time of injection could present 1-4 hours after the injection. These symptoms could include: fever, nausea/vomiting, chills/rigors, and hypotension. Subjects must remain in observation until all of these symptoms have resolved to  $\leq$  Grade 1. Refer to **Table 4.1.4-1** for current CMP-001 safety profile in the ongoing CMP-001-001 clinical study.

Subjects who experience a DLT will have dosing of CMP-001 withheld until the toxicity has returned to  $\leq$  Grade 1. If the Investigator determines that continued treatment with CMP-001 is in the subject's best interest, treatment may resume at a reduced dose of CMP-001. Only one dose reduction is allowed. Subjects who still experience DLTs at Dose Level-1 must come off study.

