#### 7.1.1 Treatment period

The study consists of 3 main phases:

- **Prime Phase (Weeks 1-7):**
  - Nivolumab (240 mg) I.V. infusion every 2 weeks for 3 doses (starting 2nd week of CMP-001 administration – W2D1) given concurrently with CMP-001.
  - CMP-001 will be administered subcutaneously (week 1), then intra-tumorally (weeks 2-7) on a weekly schedule.
- **Definitive Surgery:** Follows completion of prime phase.
- **Boost Phase (following recovery from surgery) (Weeks 12-56):**
  - Nivolumab (240 mg I.V. infusion every 2 weeks; or 480 mg I.V infusion every 4 weeks) given concurrently with CMP-001 5mg every 4 weeks.
  - CMP-001 will be administered subcutaneously (peri-tumoral resection site).
  - Total of 12 doses of CMP-001 will be administered.
  - Total of 46 weeks of Nivolumab will be administered (every 2 weeks - 23 doses; every 4 weeks – 12 doses).

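### Section 8.2 limits a DLT to the first 15 days but also monitors DLTs for 4 weeks; read literally, the rules for a DLT on a reduced CMP-001 dose cannot operate after a dose-3 DLT

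*Combined protocol and SAP*

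**What the plan says.** Section 8.2 restricts DLTs to related adverse events "which occur during the first 15 days of therapy (i.e. following 3 doses of CMP-001; W1D1, W2D1, W3D1", and to the Prime phase. The same section says that DLTs are monitored for 4 weeks in the first 3 patients, with accrual closed during monitoring. It does not say how the two periods relate, and no other section gives a different window.

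Three rules depend on whether a DLT occurs after the CMP-001 dose has been reduced:

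- **Accrual halt** (Section 8.2): "If a subject experiences DLT on a reduced dose of CMP-001, further accrual will be halted".
- **Off study** (Section 5.2.2.7): "Subjects who still experience DLTs at Dose Level-1 must come off study".
- **Re-escalation** (Section 8.2): the investigator may return to the original dose if "the lower dose level was tolerated without any DLTs" and the Sponsor approves.

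Dose reduction is foreseen well beyond day 15. Section 5.2.2 says "intra-tumoral doses during this period of the Prime Phase (weeks 2-7) may be reduced", and Section 5.2.2.4 says "CMP-001 will be dose-reduced in patients who develop CMP-001 related DLT". Section 8.2 adds that "treatment may resume at a reduced dose (2.5mg weekly or every 4 weeks; 1 dose level lower) at the same schedule". In the study calendar notes (Section 6.1) the 4-weekly CMP-001 schedule exists only in the Boost Phase.

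**The concern.** The three rules decide what happens to a patient, and possibly to accrual, when a reduced dose is not tolerated. They need a DLT on the reduced dose, but the definition stops the clock on the day of the third injection. A patient with a DLT after that injection receives every reduced dose outside the window.

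This is not a remote case. Section 4.1.4 reports that the acute reactions in the earlier CMP-001 melanoma study typically appeared after the third dose, and Section 5.2.2.7 expects cytokine-related symptoms 1 to 4 hours after an injection.

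A hypothetical example shows what is at stake. A patient has Grade 3 hypotension after dose 3, which is a DLT, and restarts on day 22 at a reduced dose.

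- If Grade 3 hypotension recurs on day 29, the note to the table in Section 5.2.1.2 stops treatment. That patient is largely protected, but the accrual halt is not triggered.
- If a different related event occurs on day 29, such as Grade 3 vomiting despite maximal treatment, it meets a listed criterion but is not a DLT under either period. CMP-001 is held, yet the off-study rule does not apply, accrual does not halt, and the DLT condition for re-escalation still reads as met.

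**Working it through.** **Inputs.** Prime Phase CMP-001 is weekly, 7 doses (Section 6.1). For the Boost Phase, Section 7.1.1 says "Total of 12 doses of CMP-001 will be administered". Planned total: 7 + 12 = 19. The window ends on day W, with W = 15 (definition) or W = 28 (4-week monitoring). After a DLT following dose k, the earliest reduced dose is taken to be dose k + 1, on schedule.

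**The plan's own figure.** Day of dose k = 1 + 7(k − 1), giving days 1, 8, 15, 22, 29, 36 and 43. Dose 3 falls on 1 + 7 × 2 = 15, so 15 days and 3 doses agree.

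**Countable days on the reduced dose** = max(0, W − day of dose k + 1, plus 1), where the day is that of dose number k + 1. Later planned doses = 19 − k.

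| First DLT after | First reduced dose | Countable days, W = 15 | Doses that can count, W = 15 | Countable days, W = 28 | Doses that can count, W = 28 |
|---|---|---|---|---|---|
| Dose 1 | Day 8 | 15 − 8 + 1 = 8 | 2 of 18 (11%) | 28 − 8 + 1 = 21 | 3 of 18 (17%) |
| Dose 2 | Day 15 | 15 − 15 + 1 = 1 | 1 of 17 (6%) | 28 − 15 + 1 = 14 | 2 of 17 (12%) |
| Dose 3 | Day 22 | 15 − 22 + 1 = −6, so 0 | 0 of 16 (0%) | 28 − 22 + 1 = 7 | 1 of 16 (6%) |

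These are upper limits, because any delay while toxicity resolves reduces them. Under the 15-day definition, only 2 of the 6 intratumoral doses (days 8 and 15) can ever count. Under either period, none of the 12 Boost doses can.

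**Sensitivity for the dose-3 case.**

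- Letting the window run until just before dose 4 (W = 21) gives 21 − 22 + 1 = 0 days.
- Giving dose 4 two days early (the Section 5.2.1.3 window) puts it on day 20, still outside. Five days early gives day 17, also outside.
- Only the full one-week rescheduling allowance in Section 6 brings dose 4 back to day 15. That allowance is for calendar problems and is not realistic after a toxicity hold.

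**Would adopting 4 weeks be enough?** No. If the definition were extended to 28 days, a DLT after dose 4 (day 22) would lead to a first reduced dose on day 29, and 28 − 29 + 1 = 0. A longer fixed window moves the gap to a later dose.

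The counts are of dose slots, not risk. The documents give neither a DLT rate for this trial nor a risk on a reduced dose, so no trial-level probability is offered.

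**The case against.** The best reply is that the literal reading is not the natural one. After the windowed definition, Section 8.2 lists the events to be treated as DLTs without repeating any time limit, and it later speaks of cases that would otherwise satisfy the DLT criteria. Reduced dosing every 4 weeks makes sense only in Boost. On that reading a DLT in the three rules is any related event meeting the listed criteria, and the rules work. This stands as the probable intent. It is nevertheless an inference against an express definition, and a mandatory off-study or halt rule should not depend on it.

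The second reply is that patients are protected anyway, and much of this stands:

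- Section 5.2.2.4 holds CMP-001 for related Grade 3 or higher non-hematologic and Grade 4 hematologic toxicity.
- Section 5.2.1.2 holds nivolumab. It requires permanent discontinuation for Grade 4 events in most rows, for Grade 3 events that recur, and for life-threatening events.
- Section 5.7 permits discontinuation for dose-limiting or other unacceptable toxicity, with no time limit.
- Section 8.7 provides weekly review and lets the DSMB or DSMC suspend accrual.
- Re-escalation is optional and needs Sponsor approval.

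These provisions do not trigger the stated halt or repair the re-escalation test. For a different second Grade 3 event, the table row for other drug-related toxicities allows restart after resolution, and the Section 5.7 ground is discretionary.

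Third, the halt rule may be spent. Section 8.2 treats 5 mg as the dose under test and 2.5 mg as one level lower, whereas Table 5.2.2.3-1 starts at 10 mg with 7.5 mg next. Section 4.2.2 describes the safety run-in in the past tense. If the halt applied only to the first 3 patients, little of it remains. The dose-reduction and off-study rules in Section 5.2.2 carry no such limit.

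**Conclusion.** The point holds as an internal conflict in the safety rules. The 15-day definition and the 4-week monitoring period disagree. Under the former, a dose-3 DLT leaves 0 of 16 later planned doses able to produce a DLT on a reduced dose; under the latter, 1 of 16, the day-22 dose. Boost doses never count. This assumes on-schedule dosing and restart no earlier than the next scheduled dose.

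A reader might infer that the trial has no working protection after day 15, or that a patient could be required to continue or go back up in dose after a second severe event. The documents do not support that: the hold, discontinuation and oversight provisions apply without the DLT label, and re-escalation remains a choice. Nor is the short window for a first DLT at fault; it is a legitimate design choice.

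Severity is minor. The primary endpoint and the Simon boundaries are unaffected.

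**What to change.** Add one sentence to Section 8.2 and repeat it in Section 5.2.2.7, along these lines:

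> Any related event that meets the DLT criteria listed in Section 8.2 while the subject is on a reduced dose of CMP-001, at any time in the Prime or Boost Phase, is a DLT for the off-study and re-escalation rules and, where it applies, the accrual-halt rule.

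In Section 8.2, also reconcile the two periods, for example by keeping 15 days for classifying a first DLT and describing the 4 weeks as the observation period for the first 3 patients during which accrual is closed. The 15-day window for a first DLT can stay.

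The cost is a few sentences. No visits are added, because adverse events are already assessed continually through 30 days after end of treatment (Section 6.1). The downside is that slightly more patients may come off study or be refused re-escalation, and accrual may halt more often if the halt rule covers all subjects. The documents do not allow the size of either increase to be estimated.

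### Section 8.2 gives a CMP-001 tested dose (5 mg) and a post-DLT restart dose (2.5 mg) that do not match the 10 mg Prime regimen or the dose-reduction table

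*Combined protocol and SAP*

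**What the plan says.** **The regimen.** Section 5.2.2 fixes the week 1 dose of CMP-001 at 5 mg subcutaneously and then states: "Subsequent doses of CMP-001 administered during the Prime Phase (weeks 2-7) will be at 10mg administered intra-tumorally". Sections 4.2.2 and 5.3 agree. After surgery, "during the Boost Phase, the CMP-001 dose is fixed at 5mg injected subcutaneously at the site of the resected tumor".

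**Reductions in Section 5.** For a CMP-001-related DLT, Section 5.2.2.4 says "In this event, CMP-001 will be dose reduced as in" Table 5.2.2.3-1. That table gives Level 1 as 10 mg, Level -1 as 7.5 mg, Level -2 as 5 mg and Level -3 as 2.5 mg. Section 5.2.2.7 adds: "Only one dose reduction is allowed. Subjects who still experience DLTs at Dose Level-1 must come off study".

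**Section 8.2.** The safety monitoring text says that "the dose being tested in this study (5mg) is 50% the ceiling dose tested in other CMP-001 studies". It counts as DLTs the related events "which occur during the first 15 days of therapy (i.e. following 3 doses of CMP-001; W1D1, W2D1, W3D1) IN the Prime phase only". For a patient who has had a DLT it provides that "treatment may resume at a reduced dose (2.5mg weekly or every 4 weeks; 1 dose level lower"), at the same schedule and after consultation with the Principal Investigator.

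**The concern.** Sections 5.2.2.4 and 8.2 both tell the investigator how to restart CMP-001 after a DLT, and neither is given precedence. Section 8.2 appears to take 5 mg as the starting dose, while Section 5 takes 10 mg. If so, a patient with a DLT on a 10 mg injection would restart at a different dose depending on which section is opened. The sentence that places the trial at half the ceiling dose would also misdescribe most of the Prime phase, and it forms part of the written safety rationale.

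**Working it through.** 1. **Ceiling implied by Section 8.2.** If 5 mg is 50% of the ceiling, the ceiling is 5 / 0.50 = 10 mg. This agrees with Section 4.1.4 (1 to 10 mg explored in the earlier melanoma study) and with the 10 mg daily maximum in Section 5.2.2.3.

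2. **Where the Prime dose stands against it.** Week 1: 5 / 10 = 50%. Weeks 2-7: 10 / 10 = 100%. Six of the seven Prime doses are at the ceiling, so the 50% statement is right only for the subcutaneous doses (week 1 and Boost).

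3. **Which doses can lead to a DLT.** The window covers W1D1, W2D1 and W3D1, that is 5 mg subcutaneous, 10 mg intra-tumoral and 10 mg intra-tumoral. Two of the three are 10 mg. Both fall within the scope of Table 5.2.2.3-1, whose title covers Prime doses 2 to 6.

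4. **Restart dose after a DLT on 10 mg.**

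| Source | Restart dose | Share of 10 mg | Table levels below 10 mg |
|---|---|---|---|
| 5.2.2.4 with Table 5.2.2.3-1, one level down | 7.5 mg | 7.5 / 10 = 75% | 1 |
| 8.2 | 2.5 mg | 2.5 / 10 = 25% | 3 (stated as 1) |

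The ratio is 7.5 / 2.5 = 3.

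5. **Could Section 8.2 be a Boost-only rule?** One table step below 5 mg is 2.5 mg, so its figure fits a 5 mg starting dose, and its four-weekly option fits Boost. But it also covers weekly dosing, which the Study Calendar Notes give for Prime only, and DLTs are counted in Prime only. The rule therefore has to work for 10 mg, and there it does not.

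6. **Off-study rule.** Section 5.2.2.7 names only Dose Level -1. In the table that is 7.5 mg. A patient restarted at 2.5 mg under Section 8.2 is at Level -3, so the label does not match.

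7. **Design figures.** Section 8.3 continues with at least 5 of 14 and declares success with at least 13 of 30. The probability of success is the sum over x1 = 5 to 14 of P(X1 = x1) × P(X2 ≥ 13 − x1), with 14 and 16 patients. It is 0.0470 at a 28% rate and 0.9073 at 55%, against the stated 5% and 0.91. Neither figure uses a CMP-001 dose.

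**The case against.** The strongest reply is that Section 8.2 describes a finished run-in. It monitors DLTs for the first three patients accrued, and Section 4.2.2 reports the run-in results in the past tense and bases the fixed Prime dose on them. On that reading Section 5.2.2.4 and the table govern reductions now. This makes the mismatch less pressing but does not remove it: the restart rule in Section 8.2 is not limited to those three patients, and Section 5.2.2.7 speaks of subjects with a DLT in general.

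Three further points stand. Following Section 8.2 gives less drug, so the risk is under-dosing. The trial is single-center and consultation is required before a restart, so the discrepancy would probably be noticed. And 5 mg is not baseless: 13 of the 19 planned CMP-001 doses are 5 mg (week 1 plus 12 in Boost).

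A reader might infer more than the documents support:

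- *That the table raises the dose after a week 1 DLT.* The table covers intra-tumoral Prime doses and not the fixed subcutaneous dose. The next planned dose is 10 mg, so 7.5 mg would still be a reduction, and Section 8.2 supplies 2.5 mg as one step below 5 mg.
- *That re-escalation conflicts with the one-reduction limit.* Section 8.2 says "The Investigator may escalate the subject back to the original CMP-001 dose level if" the lower dose was tolerated without a DLT and the Sponsor approves. Going back up is not a second reduction. More detail could be given, but the two rules do not contradict each other.
- *That a patient on 2.5 mg has no stopping rule.* Section 8.2 labels that dose one level lower, and Section 5.7 lists DLT among the grounds for discontinuation. The mismatch is in the label.

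**Conclusion.** Section 8.2 is wrong as written for the current Prime regimen. Its tested dose is half of what is given in six of seven Prime injections. Its restart dose after a DLT on 10 mg is three table levels down where it says one: 2.5 mg against the 7.5 mg that Section 5 gives. The severity is minor to moderate. That Section 8.2 is left over from an earlier dosing scheme is an inference, supported by the account in Section 4.2.2 of varied run-in doses; the contradiction does not depend on it.

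A reader might conclude that the safety case fails or that patients would be overdosed. The documents do not show this. Section 8.2 still reports no toxicity rate above 33% in the other combination studies, Section 4.2.2 reports no increase in adverse events at higher doses in the run-in, and the discrepancy points toward less drug. The sample size, type I error and power are unaffected.

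**What to change.** In Section 8.2:

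- State the dose as 10 mg intra-tumoral in Prime weeks 2-7, and 5 mg subcutaneous in week 1 and in Boost.
- Correct or delete the sentence that puts the tested dose at half of the ceiling.
- Set the reduction after a DLT on a 10 mg dose at 7.5 mg (Level -1 of Table 5.2.2.3-1). Keep 2.5 mg only as the reduction from a 5 mg subcutaneous dose.

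In Section 5.2.2.7, apply the off-study rule to a DLT at the reduced dose, in place of naming Dose Level -1 alone.

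The cost is a wording amendment to two sections. It needs no new visits or procedures and has no effect on the operating characteristics.
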